- Elderly (≥ 65 years): In general, no dosage adjustment is recommended based on age. Renal function and risk of volume depletion should be taken into account. Due to the limited therapeutic experience in patients 75 years and older, initiation of dapagliflozin therapy is not recommended.
- Patients at risk for hypotension due to effect of dapagliflozin on diuresis and blood pressure: Caution should be exercised in patients for whom a dapagliflozin-induced drop in blood pressure could pose a risk, such as patients with known cardiovascular disease, patients on anti-hypertensive therapy with a history of hypotension or elderly patients. For patients receiving dapagliflozin, in case of intercurrent conditions that may lead to volume depletion,

careful monitoring of volume status (e.g. physical examination, blood pressure measurements, and laboratory tests including haematocrit) and electrolytes is recommended. Temporary interruption of treatment with dapagliflozin is recommended for patients who develop volume depletion until the depletion is corrected.

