3.3.1 Content of the Cegedim LPDs

Data are entered during usual patient care and submitted daily to the Cegedim coordinating center, cleaned and de-identified and then made available in the LPDs for research no later than one month after submission. The following anonymized patient data collected from GPs' practice will be extracted from the databases:

- Demographics (Year of birth, gender, registration dates),
- Medical History (Event dates, diagnosis, symptoms, risk factors, co-morbidities, referrals,
- Treatments (indication, molecule/brand, dosage, posology, date and length of prescription),
- Clinical Data (Height, weight, BP, life habits),
- Clinical laboratory tests, X-ray and other investigations (not available in Germany).

The median follow-up duration of a patient in the data base is 27 months in Germany, 36 months in France, 44 months in Spain, 46 months in Belgium, 112 months in Italy and 117 months in UK.

Patient data collected by Cegedim in each country participating in the LPD varies to some extent to accommodate local needs. However, all countries collect data on medical co-morbidities and outcomes, prescriptions, demographics, and physician characteristics. Key metrics of the GPs' LPDs are provided for each country in Appendix 2 (2012 data).

In the LPDs, diagnoses of clinical events are recorded as diagnostic codes (*e.g.* ICD-9, READ). These codes from the different participating countries will be harmonized based on pre-specified algorithms developed prior to the analysis and listed in the statistical analytic plan. Table 3.3.1-1 summarizes the coding conventions for each of the databases.

Table 3.3.1-1: Data Coding Conventions in the Different Countries

	Belgium	France	UK	Italy	Germany	Spain
Drug code dictionary	Association Pharmacologique Belge	Claude Bernard	Multilex	Farmadati	Abdata	Vademecum
Therapy classification	European Pharmaceutical Marketing Research Association (EphMRA)		British National Formulary (BNF)	ATC	ATC	ATC
Disease classification	Cegedim prop thesaurus (mapped	-	Read Codes	ICD-9	ICD-10	CIAP mapped to ICD-9

ATC = Anatomic, Therapeutic, Chemical

ICD = International Classification of Disease

CIAP = International Classification of Primary Care

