3.4.1 Outcomes/Endpoint Variables

Table 3.4.1-1 includes the characteristics and definitions of how dapagliflozin users will be categorized and described.

Table 3.4.1-1: Categorization of Dapagliflozin Users

Characteristic	Definition
Patient Demographics, at initiation of dapagliflozin use:	
Age categories	< 45, 45-59, 60-74, >= 75
Sex	Male or Female
Country	Belgium, France, Germany, Italy, Spain, United Kingdom
Concomitant medications before, at initiation of and	Loop diuretics (ATC code C03Cx)
during dapagliflozin use 1	Pioglitazone (Actos, Glustin) (ATC code A10BG),
	Biguanides (ATC Code A10BA)
	Sulfonamide derivates (ATC code A10BB and A10BC)
	Dipeptidyl peptidase 4 inhibitors (DDP4) (ATC code A10BH)
	Glucagon-like peptide 1 (GLP-1, exenatide, liraglutide, ATC code A10BX),
	Alpha glucosidase inhibitors (ATC code A10BF).
	Insulin (ATC code A10A)
Concomitant co-morbidities, at initiation of dapagliflozin use:	
Baseline history of moderate renal impairment	CrCl or eGFR ² value between 30-60 within 12 months prior to the dapagliflozin dispensing
Baseline history of severe renal impairment	CrCl or eGFR value < 30 within 12 months prior to the dapagliflozin dispensing
Baseline history of renal failure	Diagnosis codes for end stage renal disease or dialysis (see Appendix 3)
Congestive heart failure	Diagnosis codes for congestive heart failure (see Appendix 3)
Hypertension	Diagnosis codes for hypertension (see Appendix 3)
Type 2 Diabetes Mellitus, at initiation of dapagliflozin use:	Diagnostic code for T2DM within 12 months prior to the dapagliflozin dispensing (see Appendix 3) OR
	Prescription for an antiglycemic medication within 12 months prior to the dapagliflozin dispensing

Table 3.4.1-1: Categorization of Dapagliflozin Users

Characteristic	Definition
Dapagliflozin Dose, at initiation of dapagliflozin	10 mg
use:	5 mg
Off-Label Use	Patients meeting one of the following criteria:
	 17 years old or younger on index date
	• 75 years of age or older on index date
	 No diagnostic codes for Type 2 Diabetes Mellitus, at or before the initiation of dapagliflozin use (see definition above)
	• Baseline history of moderate renal impairment (see definition above)
	• Baseline history of severe renal impairment (see definition above)
	• Baseline history of renal failure (see definition above)

^[1] Pioglitazone sales are suspended in France and Germany

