APPENDIX 3 CODE LISTS

	ICD9	ICD10
T2DM	250.x0	E10.x
Acute renal failure	584.x	N17.x
Severe chronic renal failure	585.x	N18.3, N18.4, N18.5
U failure	586.x	N19.
Dialysis	V45.11, V56.x	Y84.1
Renal transplantation	E878.0	Y83.0
Congestive heart failure	428.0	150.0
Hypertension	401.x	I10.x, I11.x, I12.x, I13.x, I15.x

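### Appendix 3 defines hypertension more narrowly in ICD-9 (401.x only) than in ICD-10 (I10-I13 and I15), so part of any country difference in baseline hypertension would come from the definition

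*Protocol*

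**What the plan says.** Protocol section 3.4.1, Table 3.4.1-1, lists hypertension among the co-morbidities recorded when dapagliflozin is started. Its whole definition is "Diagnosis codes for hypertension (see Appendix 3", so the appendix is the operative definition.

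Appendix 3 has an ICD-9 column and an ICD-10 column. The hypertension row is "Hypertension 401.x I10.x, I11.x, I12.x, I13.x, I15.x".

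Table 3.3.1-1 (section 3.3.1) gives the disease classification used in each database. For the UK, Italy, Germany and Spain, in that order, it reads "Read Codes ICD-9 ICD-10 CIAP mapped to ICD-9". Belgium and France use a proprietary thesaurus. Section 3.3.1 also says that diagnostic codes from the different countries will be "harmonized based on pre-specified algorithms developed prior to the analysis and listed in the statistical analytic plan".

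Section 2.1 makes the description of new users by country and by selected co-morbidities part of the primary objective. Section 4.1.1 repeats this for the analysis and plans no formal comparative tests.

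**The concern.** The two columns of one row should describe the same condition in two coding systems. Here they do not: the ICD-10 list takes in categories whose ICD-9 counterparts are absent. If the appendix is applied as printed, a patient recorded only with hypertensive heart disease, hypertensive renal disease or secondary hypertension is hypertensive in the German data and not hypertensive in the Italian or Spanish data.

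What is at stake is how a descriptive table by country is read. A lower hypertension percentage in Italy or Spain than in Germany could reflect different patients, different recording habits or the narrower list. The table alone would not let a reader separate the third cause from the other two.

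**Working it through.** The plan states no figure for this point, so there is none to reproduce. The check compares the two columns, links them to countries, and then gives a range for the possible size.

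**Step 1: compare the columns.** Appendix 3 prints codes without titles. The match below uses the standard titles of the two classifications.

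| Condition | ICD-10 code, listed? | ICD-9 counterpart, listed? |
|---|---|---|
| Essential hypertension | I10, yes | 401, yes |
| Hypertensive heart disease | I11, yes | 402, no |
| Hypertensive renal disease | I12, yes | 403, no |
| Hypertensive heart and renal disease | I13, yes | 404, no |
| Secondary hypertension | I15, yes | 405, no |

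ICD-10 has five categories and ICD-9 has one. The shortfall is on the ICD-9 side only.

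**Step 2: link the columns to countries.** The systems come from Table 3.3.1-1 and the forecast users from the totals in Table 4.2-1.

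- ICD-9 (Italy, and Spain by mapping): 2728 + 646 = 3374; 3374 / 20325 = 16.6%.
- ICD-10 (Germany): 3871 / 20325 = 19.0%.
- Read codes (UK): 2723 / 20325 = 13.4%.
- Proprietary thesaurus (France and Belgium): 9246 + 1111 = 10357; 10357 / 20325 = 51.0%.

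Check: 3374 + 3871 + 2723 + 10357 = 20325, the stated total. The direct contrast is therefore between databases holding 16.6% and 19.0% of forecast users. For the UK, Appendix 3 has no column, so a Read list would have to follow one of two unequal scopes.

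**Step 3: size under stated assumptions.** Let p be the true prevalence of hypertension in the broad (ICD-10) sense, and u the fraction of hypertensive patients whose only hypertension code lies outside essential hypertension. A patient who also has a 401 code is still counted. Then

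ICD-9 shortfall = p × u.

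Neither p nor u is in the documents. Assumed ranges are p = 50-70% and u = 1-10%.

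| p | u = 1% | u = 5% | u = 10% |
|---|---|---|---|
| 50% | 0.5 points | 2.5 points | 5.0 points |
| 60% | 0.6 points | 3.0 points | 6.0 points |
| 70% | 0.7 points | 3.5 points | 7.0 points |

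The range is 0.5 to 7 percentage points. If general practitioners code most hypertension as essential, the true value lies near the lower end.

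**The case against.** **The SAP may repair it.** Section 3.3.1 defers harmonisation of country codes to the SAP, which is not shown. Appendix 3 has no column for Read codes or the thesaurus, so it cannot be the complete operational list. This is the best argument against the point, and it lowers the severity. It does not remove the point, because the protocol does not leave hypertension open: it fixes two unequal lists and names them as the definition. A SAP that follows Appendix 3 inherits the mismatch, and one that corrects it departs from Table 3.4.1-1.

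**The reach is limited.** Section 1.1 says reimbursement was undetermined in Italy and Spain, and that Germany reimbursed the drug only for 2013. The UK, where reimbursement was achieved, uses neither column directly. The Synopsis plans statistics within each database. Hypertension is not in the off-label definition or among the four subgroups named in section 2.1. All of this stands.

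**Stronger readings that the documents do not support.**

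- A reader might infer that the heart-failure row has the same fault, or that it undercounts heart failure. The row is "Congestive heart failure 428.0 150.0". It pairs one code with one code; the printed 150.0 is plausibly I50.0 misread from the PDF. The two are like-for-like. The variable is labelled congestive heart failure, and the narrow list fits that label. Nothing says all heart failure was meant, so widening the list would redefine the variable, not correct a shown error.
- A reader might infer that the mismatch hides a group at risk of volume depletion. The Introduction lists "patients with known cardiovascular disease, patients on anti-hypertensive therapy with a history of hypotension or elderly patients" as groups for whom a fall in blood pressure could pose a risk. Its advice on volume depletion is separate and concerns intercurrent conditions.
- A reader might infer that it affects the findings on loop diuretics. Research question 4 asks only for a proportion of users and does not use hypertension.

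**Conclusion.** The point holds for hypertension alone. As printed, Appendix 3 gives Italy and Spain a narrower hypertension variable than Germany, and the direction is clear: some hypertensive patients are missed on the ICD-9 side. The size is about 0.5 to 7 percentage points if prevalence is 50-70% and 1-10% of hypertensive patients are coded only outside essential hypertension. Both ranges are assumptions, and the effect may well be modest. It also depends on the SAP algorithms, not shown, applying the appendix as written. One descriptive co-morbidity row is affected, with no test and no off-label count involved. Severity is low, but the correction is simple and should be made.

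**What to change.** Before data extraction, make the two sides of the hypertension row equal in one of two ways:

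- set ICD-9 to 401.x-405.x, to match I10-I13 and I15; or
- restrict ICD-10 to I10.x, to match 401.x.

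Use the chosen scope for the UK Read list and the Belgian and French thesaurus lists, and write it into the SAP harmonisation algorithms so that protocol and SAP agree. Leave the heart-failure scope as it is, but check the printed 150.0 against the source file.

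The cost is an edit to a code list. It needs no new data and changes no other analysis. The first option keeps the broader variable already set for Germany; the second narrows it there to essential hypertension.

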APPENDIX 4 MDRD GFR EQUATION

GFR = 175 x SerumCr-1.154 * age-0.203 * 1.212 (if patient is black) * 0.742 (if female)

Date: 13-Nov-2013

APPENDIX 5 COCKROFT & GAULT FORMULA

Cl_{cr} = Estimated creatinine clearance (ml/min.)

Age = Age in years

Weight = Body weight (Kg)

[Cr] = Serum creatinine (μ mol/L)

K = 1.
$$Cl_{Cr} = \frac{(140 - Age) \times Weight}{7.2 \times [Cr]} \times k$$
 23 (men) or 1.04 (women)

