Estimated creatinine clearance (CrCl) will be calculated by means of the Cockcroft-Gault formula if it is not available in the database. (Appendix 5)

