4 STATISTICAL ANALYSIS

4.1 Statistical Analysis Methods

The details of the data analysis will be documented in a Statistical Analysis Plan (SAP) document, which will be finalized before the first extraction of data from the databases. The SAP will elaborate on the analytic plans outlined in the protocol; any major modifications will be reflected in a protocol amendment.

The goal of the analyses is to describe the characteristics of patients who use dapagliflozin.

Since the study is purely descriptive, missing data will not be imputed but the amount of missing data will be reported for each variable.

^[2] eGFR will be estimated by the creatinine clearance calculated by means of the Cockroft & Gault formula if it is not available in the data base.

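### The Cockcroft-Gault formula in Appendix 5 converts units twice, so every clearance calculated from it is 7.2 times too low

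*Protocol*

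**What the plan says.** Appendix 5 of the protocol prints the formula

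Cl = (140 − Age) × Weight ÷ (7.2 × [Cr]) × k.

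The output is "Estimated creatinine clearance (ml/min" and the creatinine input is "Serum creatinine (μ mol/L". The constant k is 1.23 for men and 1.04 for women. The text layer gives this as "23 (men) or 1.04 (women", with the 1. stranded before the equation. That split is an artefact of reading the PDF and is not part of the complaint.

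The appendix is operative. The notes to Table 3.4.1-1 in Section 3.4.1 say "Estimated creatinine clearance (CrCl) will be calculated by means of the Cockcroft-Gault formula if it is not available in the database" and point to Appendix 5. Footnote 2 of the same table extends this to eGFR: "eGFR will be estimated by the creatinine clearance calculated by means of the Cockroft & Gault formula" when none is recorded.

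Table 3.4.1-1 then classifies the result. Moderate impairment is a "value between 30-60 within 12 months prior to the dapagliflozin dispensing", and severe impairment is a "CrCl or eGFR value < 30 within 12 months prior to the dapagliflozin dispensing". Both categories also count as off-label use.

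**The concern.** The 7.2 divisor, the µmol/L unit and the constants 1.23 and 1.04 do not belong to the same version of Cockcroft-Gault. The constants go with creatinine in µmol/L and no further divisor. The 7.2 goes with creatinine in mg/L and no such constants. Printed together, they scale the result twice.

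The calculated value feeds research question 2 (the proportion with moderate to severe renal impairment), the moderate and severe renal subgroups of the primary objective, and the off-label proportion. These are central outputs of a study done at regulatory request (Section 1.1) and reported to the CHMP (Section 4.3). A downward error of this size would make patients with normal renal function appear severely impaired.

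**Working it through.** The protocol gives no numerical result from this formula, so there is no figure of its own to reproduce.

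**Inputs.** From Appendix 5: divisor 7.2, creatinine in µmol/L, k = 1.23 or 1.04. From Table 3.4.1-1: cut-offs 30 and 60. From Appendix 4: the MDRD equation, which states no creatinine unit; mg/dL is assumed. Not in the protocol: the standard mg/dL form of Cockcroft-Gault, (140 − age) × weight ÷ (72 × Cr), × 0.85 for women, and 1 mg/dL = 88.4 µmol/L.

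**Step 1: what k contains.**
- Men: 88.4/72 = 1.228, which rounds to 1.23.
- Women: 0.85 × 88.4/72 = 1.044, which rounds to 1.04.

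So k is the full conversion. With creatinine in µmol/L the denominator should be [Cr] alone.

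**Step 2: example patients.**

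| Patient | Without the 7.2 | As printed |
|---|---|---|
| Man, 60 y, 90 kg, 80 µmol/L | (80 × 90/80) × 1.23 = 110.7 | 110.7/7.2 = 15.4 |
| Man, 30 y, 80 kg, 80 µmol/L | (110 × 80/80) × 1.23 = 135.3 | 18.8 |
| Woman, 60 y, 75 kg, 65 µmol/L | (80 × 75/65) × 1.04 = 96.0 | 13.3 |
| Woman, 75 y, 70 kg, 110 µmol/L | (65 × 70/110) × 1.04 = 43.0 | 6.0 |

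The ratio is 7.2 for every patient.

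**Step 3: comparison with Appendix 4.** For a man aged 60, 85 kg, 80 µmol/L:
- Appendix 5 as printed: 14.5.
- Appendix 5 without the 7.2: 104.5.
- Standard mg/dL form: 104.4.
- Appendix 4 MDRD: 175 × (80/88.4)^−1.154 × 60^−0.203 = 85.5.

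As printed, the two appendices differ about sixfold for this man (85.5/14.5 = 5.9).

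**Step 4: what the cut-offs then mean.** A printed value below 30 corresponds to a true clearance below 30 × 7.2 = 216 ml/min. A printed value below 60 corresponds to one below 60 × 7.2 = 432. A truly moderate patient (30 to 60) gets 4.2 to 8.3 and is always classed severe. To reach 60 as printed, a 60-year-old man of 90 kg would need creatinine of 80 × 90 × 1.23/(7.2 × 60) = 20.5 µmol/L.

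**Step 5: effect on a population.** Three simulated mixes of 400,000 patients each, 45% women. Age and weight are normal. Creatinine is lognormal around the centre shown, multiplied by 1.05 for men and 0.82 for women. All of these are assumptions.

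| Mix: mean age, mean weight, creatinine centre | Median true CrCl | Printed <30 | Printed <60 | True <30 | True 30–60 |
|---|---|---|---|---|---|
| Base: 60 y, 88 kg, 78 µmol/L | 107 | 98.0% | >99.9% | 0.04% | 5.9% |
| Younger, heavier: 52 y, 100 kg, 70 µmol/L | 150 | 87.8% | 99.98% | about 0% | 0.5% |
| Older: 68 y, 80 kg, 85 µmol/L | 81 | 99.6% | about 100% | 0.7% | 21.9% |

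**The case against.** The arithmetic is not in dispute. The case on the other side concerns reading, reach and practical risk.

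- **The unit may be the slip.** If mg/L was meant, the printed formula is too high rather than too low: by 23% for men (1.23/1) and 22% for women (1.04/0.85). This should be acknowledged, but it does not rescue the appendix, because divisor, unit and constants are incompatible on either reading.
- **Only calculated values are affected.** This stands. Recorded CrCl or eGFR values are untouched, and renal failure is defined by diagnosis codes. The size of the affected group is unknown, because Table 3.3.2-3 pools recorded and calculated eGFR. In Germany 52% of T2DM patients have an eGFR but only 29.1% have a weight recorded in the year (Table 3.3.2-2). So at least about 23 percentage points of those values cannot come from this formula with a same-year weight. In the UK, the other main source for renal analyses, 83.5% have a weight, so no such limit applies.
- **MDRD is also mentioned.** The footnote to Table 3.3.2-3 allows it, but footnote 2 of Table 3.4.1-1 names only Cockcroft-Gault for the study variable.
- **A programmer would use the standard form, or notice the result.** Possibly. However, the protocol cites Appendix 5 as the definition, Section 4.1 has the SAP elaborate on the protocol, and Section 6.2 requires conduct as described. Correcting it at analysis would be an unplanned change to a key variable.

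**Conclusion.** The formula is wrong as printed and must be corrected. The factor of 7.2 is exact and the same for every patient whose clearance is calculated from Appendix 5 with creatinine in µmol/L. It rests only on the standard form of Cockcroft-Gault and the factor 88.4. The share misclassified depends on case mix: in the assumed mixes, about 88% to 99.6% of calculated values fall in the severe category and practically all fall below 60. The moderate and severe categories, research question 2 and the off-label proportion are exposed. Code-defined renal failure and patients with recorded values are not.

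**What to change.** In Appendix 5, delete the 7.2 and print CrCl = (140 − Age) × Weight × k ÷ [Cr], with [Cr] in µmol/L and k = 1.23 (men) or 1.04 (women). An equivalent form is (140 − Age) × Weight ÷ (72 × Cr in mg/dL), × 0.85 for women. If the 7.2 is kept, the unit must become mg/L and k must become 1 (men) and 0.85 (women).

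Add one worked example as a programming check, such as the man aged 60, 90 kg, 80 µmol/L, giving 110.7 ml/min. Confirm that creatinine from each country's database is converted to the stated unit before the formula is applied.

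The cost is one line in the appendix and one in the analysis program. Design and data collection do not change.
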